	Correlation between anti-HPV IgG antibody concentration and anti-HPV neutralizing antibody titers at Day 1, Month 2, Month 3 and Month 7.

¹ Seroconversion is defined as the appearance of antibodies (i.e., concentrations/titer greater than or equal to the cut-off value) in the serum of participants seronegative before vaccination.

Note: Tertiary objectives and endpoints are available in the main text of this protocol.

Overall Design: This will be a phase 1/2 randomized, observer-blind, multi-country study with 4 groups of females 16-26 years of age at the time of vaccine administration. Participants will be

² At least 150 participants in each group. In case of any delay, analysis may be performed for as many participants as possible with data available at the time of the analysis. Analysis for remaining participants will be performed at the time of the next analysis.

³ 384 participants (at least 96 participants in each group)

randomized in a 1:1:1:1 ratio to receive a series of 3 investigational adjuvanted intervention doses (3 different potencies [a high, medium, low potency]) or a series of the *Gardasil 9* vaccine. The investigational adjuvanted intervention or *Gardasil 9* vaccine will be administered intramuscularly (IM) at Day 1 (Month 0), Month 2, and Month 6. Blood sampling will be performed on Day 1, Month 2, Month 3, Month 6, Month 7, and Month 12 to assess for immunological response. In Germany, only adult participants between and including 18 years to 26 years of age are to be included in this clinical study.

This study is organized in to 2 steps. Forty-eight participants (12 per group) of the study Step 1 (sentinel participants) will receive the initial assigned dose prior to participants in Step 2 of the study, and sentinel participants will have an additional blood sampling visit at Day 7 to assess for biochemical and hematological parameters. The internal Safety Review Committee (iSRC) will review the accumulated safety data up to 7 days post-dose 1 for the sentinel participants* to determine whether any of the pre-defined holding rules have been met. If no safety concerns were observed and no holding rules were met, the sentinel participants will continue with study visits and dosing as scheduled and the Step 2 participants will be initiated. Vaccination of Step 2 participants with a second dose will not be initiated before all Step 1 participants have received their second vaccination dose.

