17.2.3. Analysis of Secondary Safety and Reactogenicity Variables

17.2.3.1. SOLICITED EVENTS

For each study group and overall and each solicited event, the incidence rate (frequencies and percentages) of vaccinated participants with solicited administration site events (pain at injection site, redness at injection site and swelling at injection site) and systemic events (fever, headache, myalgia, arthralgia and fatigue) within 7 days after

Document: \\quintiles.net\Enterprise\Apps\sasdata\SAS\\SAS\GlaxoSmithKline\HPV\213749

(HPV9)\Biostatistics\Documentation\SAP\GSK 213749(HPV9-AS04-

001)_WZA97329_SAP_Final_v3.0_02FEB2024.docx

Author: PPD Version Number: 3.0

Version Date: 02FEB2024

Template No.: CS_TP_BS016 Revision 7 Reference: CS_WI_BS005

Page 46 of 48

each vaccine administration will be summarized (any, leading to medical advice) over the whole vaccination course with the exact 95% CI. The completeness defined as the percentage of vaccinated participants who documented presence/absence of each event as well as the daily prevalence of each symptom among vaccinated participants who documented presence /absence of the event on that day will be provided. The percentages will be out of the number of participants who have at least one documented event (either present or absent). The number of solicited events will be summarized at the maximum severity per participant. Each solicited event will be counted once regardless of the number of days the event occurred. The number of solicited events will also be summarized by severity. The percentages will be out of the number of participants in the ES for each period (after first vaccine dose, after second vaccine dose, after third vaccine dose, overall (dose) and overall (participant)) expect the overall dose. The overall dose will be out of the total number of doses in the ES.

The duration of each Grade 3 solicited event (split between solicited administration events and systemic events) will be summarized. The duration of the event is defined as the number of days that a participant had an event, for example if an event occurs on day 2 and 4 but the event did not occur on day 3 (or was not captured in the eDiary) then the duration is considered as 2 days. The duration will be summarized numerically (with n, mean, STD, median, minimum and maximum) and also the frequency (the number of events that had a duration of 1, 2, 3,4, >=5 days).

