Day 3	N* n (응)	XXX	x x (x.x)	XXX	x x (x.x)	XXX	x x (x.x)	XXX X X (X.	x) xxx	x x (x
Day 4	N* n (%)	XXX	x x (x.x)	XXX	x x (x.x)	XXX	x x (x.x)	xxx x x (x.	x) xxx	x x (x
Arthralgia	N* n (%)	XXX	x x (x.x)	XXX	x x (x.x)	XXX	x x (x.x)	xxx x x (x.	x) xxx	x x (x
Day 1	N* n (%)	XXX	x x (x.x)	XXX	x x (x.x)	XXX	$x \times (x.x)$	XXX X X (X.	xxx xxx	x x (x
Day 2	N* n (%)	XXX	x x (x.x)	XXX	x x (x.x)	XXX	x x (x.x)	XXX X X (X.	x) xxx	х х (х
Day 3	N* n (%)	XXX	x x (x.x)	XXX	x x (x.x)	XXX	$x \times (x.x)$	XXX X X (X.	xxx xxx	x x (x
Day 4	N* n (%)	XXX	x x (x.x)	XXX	x x (x.x)	XXX	x x (x.x)	XXX X X (X.	x) xxx	х х (х
Fatique	N* n (%)	xxx	x x (x.x)	xxx	x x (x.x)	xxx	x x (x.x)	XXX X X (X.	x) XXX	х х (х
Day 1	N* n (%)	XXX	x x (x.x)	XXX	x x (x.x)	XXX	x x (x.x)	XXX X X (X.	/	x x (x
Day 2	N* n (%)	xxx	x x (x.x)	xxx	x x (x.x)	xxx	x x (x.x)	XXX X X (X.	/	x x (x
Day 3	N* n (%)	XXX	x x (x.x)	XXX	x x (x.x)	XXX	x x (x.x)	XXX X X (X.	/	x x (x
Day 4	N* n (%)	XXX	x x (x.x)	XXX	x x (x.x)	XXX	x x (x.x)	XXX X X (X.	/	x x (x

Source: Listing xx.x.x.x

Abbreviations: HPV = Human Papillomavirus.

N is the number of participants in the Exposed Set for each period except Overall dose, where N is the total number of doses in the Exposed Set.

Document: \\quintiles.net\Enterprise\Apps\sasdata\SAS\SAS\GlaxoSmithKline\HPV\213749 (HPV9)\Biostatistics\Documentation\SAP\Shells\

GSK 213749(HPV9-AS04-001)_WZA97329_TFL Shells_V3.0_05FEB2024.docx

Author: Version Number: 3.0

GlaxoSmithKline Biologicals SA PROTOCOL 213749 (HPV9)

Table 14.3.2.6.2

eDiary Collection, Compliance and Completeness in Solicited Events by Intervention Group and overall Exposed Set

Period: After first vaccine dose	After second vaccine	dose / After third	vaccine dose / Overa	ll (dose) / Overall	(participant)
	HPV9 High	HPV9 Medium	HPV9 Low	Gardasil 9	Total
	N	N	N	N	N

 N^* is the number of participants with documented absence or presence of the event on that day. n is the number of participants with documented presence of the event in the Exposed Set for each period except Overall dose, where n is the total number of doses in the Exposed Set where there is documented presence of the event. Percentages are calculated as $100 * n/N^*$

Programming Notes
All events will go up to day 7.

Output ID: SE0005

[Source: \\quintiles.net\Enterprise\Apps\sasdata\SASb\SAS\GlaxoSmithKline\HPV\213749

(HPV9) \Biostatistics\Filename.sas] IQVIA DDMMMYYYY HH:MM

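### In shell Table 14.3.2.6.2, the Overall (dose) panel divides doses with a symptom by participants with a diary entry, inflating daily prevalence by up to a factor of three

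*SAP*

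**What the plan says.** SAP 17.2.3.1 promises two diary summaries. One is completeness, the share of vaccinated participants who recorded each event as present or absent. The other is the "daily prevalence of each symptom among vaccinated participants who documented presence /absence of the event on that day will be provided". The next sentence reads: "The percentages will be out of the number of participants who have at least one documented event (either present or absent". Later in the paragraph, in the sentences on incidence, percentages are out of the Exposed Set for each period, with total doses as the denominator for Overall (dose).

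The TFL shells turn this into two tables, each with five period panels: after doses 1, 2 and 3, Overall (dose) and Overall (participant).

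- **Table 14.3.2.6.2 (daily prevalence).** N is participants "for each period except Overall dose, where N is the total number of doses in the Exposed Set". n is participants with the symptom, "except Overall dose, where n is the total number of doses in the Exposed Set where there is documented presence of the event". N* is the "number of participants with documented absence or presence of the event on that day", with no exception for Overall (dose). The percentage is 100 × n/N*.
- **Table 14.3.2.6.1 (completeness).** N is Exposed Set participants, switching to doses for Overall (dose). n is participants with an entry on at least one day, with no switch. The percentage is 100 × n/N.

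**The concern.** In the daily-prevalence table two of the three counts move to doses for the pooled panel, and the one that does not is the divisor. The numerator can then hold up to three diary-days per woman and the denominator only one. The result is neither a per-dose nor a per-woman prevalence.

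Large values would show themselves by passing 100%. Smaller ones would not: a true 10% shown as 30% looks ordinary in a reactogenicity table. The factor also depends on diary completion, so it need not be the same in every group.

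This is the only day-by-day prevalence table among the shells. The formulations are first-in-human, and safety and reactogenicity is one of the primary objectives, so readers are likely to consult the pooled panel for the time course of symptoms.

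**Working it through.** The plan prints no figure for either table, so there is nothing to reproduce. The check is on units.

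**Inputs**
- Doses per woman: 3 (Protocol 1.1, "to receive a series of 3 investigational adjuvanted intervention doses").
- Women per group: about 270 (SAP 4.1).
- Definitions of n, N and N*: footnotes of the two shells.
- Diary completion and dose attrition: not in the documents, so assumed below.

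**Daily prevalence, Overall (dose)**

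Printed % = 100 × (doses with symptom) / (participants with an entry that day).

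Like-for-like % = 100 × (doses with symptom) / (doses with an entry that day).

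Inflation factor = (doses with an entry) / (participants with an entry), at most 3. The printed value passes 100% once true prevalence exceeds 1/factor.

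| Assumption | Doses with entry | Participants with entry | Factor | True prevalence that prints 100% |
|---|---|---|---|---|
| All doses given, all diaries complete | 810 | 270 | 3.00 | 33.3% |
| Doses given to 270/257/243 (assumed) | 770 | 270 | 2.85 | 35.1% |
| Completion 90/85/80%, nested (assumed) | 689 | 243 | 2.84 | 35.3% |

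If entries are instead made independently after each dose with probability q (assumed), the factor is 3q / (1 − (1 − q)³): 2.70 at q = 0.9, 2.42 at 0.8 and 1.71 at 0.5. The corresponding 100% thresholds, 1/factor, are 37.0%, 41.3% and 58.3%.

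Examples with 270 women and complete diaries:
- True 10%: 81/810 = 10.0%, printed as 81/270 = 30.0%.
- True 40%: 324/810 = 40.0%, printed as 324/270 = 120.0%.
- True 50%: 405/810 = 50.0%, printed as 405/270 = 150.0%.

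**The other four panels.** n and N* are both participants, so the percentage cannot exceed 100%.

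**Completeness, Overall (dose)**

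Printed % = 100 × (participants with any entry) / (doses). With perfect diaries and three doses each this is 270/810 = 33.3%, where the answer should be 100%.

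**Does another passage supply a dose-level N*?** No. SAP 17.2.3.1 gives a dose denominator only in its incidence sentences, and that is all doses. Used here, it would count doses with no entry that day as symptom-free, against the definition of daily prevalence in the same paragraph. The N* footnotes in Tables 14.3.1.2.3 and 14.3.1.3.3 do carry an Overall (dose) exception, although the period headers of those tables list no such panel. The clause appears where it is not needed and is missing where it is.

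**The case against.** The best reply is that this is a missing clause and that nobody intends to divide doses by women. N and n both switch to doses, the sister tables carry the exception, and an experienced programmer may supply it. N is printed beside N*, so with full diaries a row showing about 810 next to about 270 should be noticed in output review. All of that is fair and bears on severity. It does not remove the fault: SAP section 9 makes the templates the description of table format and content, and the literal footnote gives the wrong divisor.

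Three stronger readings are tempting, and the documents do not support them.

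- **That completeness is always 100%.** A reader might infer this by applying the at-least-one-entry sentence in SAP 17.2.3.1 to completeness, since numerator and denominator would then be the same women. But the completeness shell divides by the Exposed Set, and the SAP defines completeness among vaccinated participants. A woman with no entries lowers the figure. The shell's actual fault runs the other way, and only in the Overall (dose) panel.
- **That late-day prevalence is understated.** The same sentence, applied to daily prevalence, would count days without an entry as observed. If 15% of women with some entries had none on Day 7, that day's figure would be 15% too low in relative terms. The 15% is only an assumption, and both the preceding SAP sentence and the N* footnote require an entry on that day. This is a conflict of wording, not a demonstrated bias.
- **That the reactogenicity time course is lost.** The by-dose panels show it correctly, Tables 14.3.1.2.2 to 14.3.1.3.3 include Grade 3 duration, and Listings 16.2.7.1 and 16.2.7.2 give daily data.

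**Conclusion.** The unit mismatch is real and confined to the Overall (dose) panels of two tables. In Table 14.3.2.6.2 daily prevalence is inflated by the ratio of documented doses to documented participants. The bound is exactly 3, reached only with complete three-dose diaries; the assumed incomplete patterns above give 1.71 to 2.85. Values over 100% need a true per-dose prevalence above about one third with complete data, and higher as completion falls. The documents give no symptom rates, so whether an impossible value would actually be printed is unknown. In Table 14.3.2.6.1 the same panel is deflated, to 33.3% at best when every woman has three doses.

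Both results assume that the footnotes are programmed literally. Severity is minor: the outputs are descriptive and secondary, the other four panels of each table match units, and neither the primary Grade 3 solicited rates nor any immunogenicity result is touched.

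**What to change.** 1. **Table 14.3.2.6.2.** Add an exception to the N* footnote: for Overall (dose), N* is the number of doses with an entry for the event on that day, whether present or absent. The panel then equals per-dose daily prevalence and cannot exceed 100% (405/810 = 50.0% in the example above).
2. **Table 14.3.2.6.1.** Add the matching exception to n: for Overall (dose), n is the number of doses for which the event was recorded as present or absent on at least one day. N already counts doses there.
3. **SAP 17.2.3.1.** Delete the sentence that makes participants with at least one documented entry the denominator, or attach it to a named output to which it applies. As placed, it conflicts with the day-specific denominator for daily prevalence and with the Exposed Set denominator in the completeness shell.

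The cost is two footnote clauses and one SAP sentence, with a matching check of the table programs. No data collection or sample size changes.
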